Very limited background information is available in the literature for the incidence rates of acute pancreatitis, pancreatic cancer and thyroid cancer, in particular medullary thyroid cancer in adult type 2 diabetes patients treated with GLP-1 agonists (i.e., exenatide and liraglutide) and other anti-diabetics. Therefore, the data from such a study will help contextualize these events expected to be observed in the patient registry of lixisenatide.

II.8. Research Question and Objectives

A series of cohort studies will be conducted based on prescription databases in Denmark, Norway, and Sweden, with a view to country-specific analysis and a planned meta-analysis of the three studies.

The primary objectives of this study are to estimate:

- 1. Incidence rates of acute pancreatitis (ICD10 K85) among adult type 2 diabetes patients treated with GLP-1 receptor agonists (i.e. exenatide and liraglutide), as well as patients treated with other anti-diabetic drugs and to examine the risk of acute pancreatitis in users of GLP-1 receptor agonists compared to users of other anti-diabetic medications;
- 2. Incidence rates of pancreatic cancer (ICD10 C25) among adult type 2 diabetes patients treated with GLP-1 receptor agonists (i.e. exenatide and liraglutide), as well as patients treated with other anti-diabetic drugs and to examine the risk of pancreatic cancer in users of GLP-1 receptor agonists compared to users of other anti-diabetic medications;
- 3. Incidence rates of thyroid cancer (ICD10 C73) (especially medullary thyroid cancer) among adult type 2 diabetes patients treated with GLP-1 receptor agonists (i.e. exenatide and liraglutide), as well as patients treated with other anti-diabetic drugs and to examine the odds ratio of medullary thyroid cancer in users of GLP-1 receptor agonists compared to users of other anti-diabetic medications.

This study is designed to focus on the risk associated with use of GLP-1 agonists and will investigate the following primary hypotheses:

- 1. That adult patients prescribed GLP-1 RAs have an increased risk of acute pancreatitis when compared to patients prescribed other types of anti-diabetic drugs;
- 2. That adult patients prescribed GLP-1 RAs have an increased risk of pancreatic cancer when compared to patients prescribed other types of anti-diabetic drugs;

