A potentially major issue surrounds the well-documented under-diagnosis of pancreatic cancer in some Cancer Registries. Kilander et al (2012) recently examined this situation in the Swedish Cancer Registry. From a total of 31,067 cases of pancreatic cancer, 44% were registered in the Hospital Patient Discharge Register but not in the Cancer Registry indicating an overwhelming under-reporting of pancreatic cancer in the Cancer Registry. Thus, diagnoses of pancreatic cancer will be sought in both the Cancer Registry and the Hospital Patient Discharge Registry in each of the countries.

Covariates

The key variables in the study will be obtained from the prescription databases (age, gender, insulin and other diabetes medications and other prescriptions); the hospital discharge registries (date of diagnosis, gallstones and obstruction of the pancreatic duct); the cancer registries (date of diagnosis, cancer site, histology and outcome of cancer); and the national death registers (date and cause of death).

All analyses will be stratified by age and gender and in addition by treatment history.

In order to improve the analysis all efforts will be made to collect additional information on several other potential confounding variables.

Potential confounders for pancreas cancer will include smoking history, alcohol intake, family history of pancreas cancer, a previous diagnosis of Multiple Endocrine Neoplasia (especially MEN1) and chronic pancreatitis.

Potential confounders for acute pancreatitis will include duration of diabetes, presence of gallstones, prior use of anti-diabetic medications, alcohol intake and obstruction of the pancreatic duct.

Potential confounders for thyroid cancer will include duration of diabetes, prior use of anti-diabetics, radiation treatment to the head and neck, iodine intake, hormonal and reproductive treatment, history of goiter or benign thyroid nodules, history of cancer, diagnosis of Multiple Endocrine Neoplasia type 2 (MEN2), and family history of medullary thyroid cancer at the baseline.

The availability of these additional data will differ between the individual countries. A dictionary of compatible covariate information will be compiled at the outset of the study to enable information common to more than one study to be collected and recorded in a manner that will enable the data to be used across studies.

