The Swedish cohort will comprise patients included in the Prescribed Drug Register, who have been prescribed GLP-1 agonists or other anti-diabetic drugs. By linkage to the regional cancer registries in Sweden as well as hospital discharge registries, information on cancer incidence and pancreatitis will be obtained.

Sweden has a highly efficient National Population and Death Register where record linkage has been done effectively on such studies. This gives coverage of all deaths in Sweden and the ability for record linkage ensures that all members of the cohort who die can be identified. In addition, Sweden has a number of other national registers that may be used to add information on potentially confounding factors.

Overall

The personal identification number will be used to link unambigously the databases in each country. The ATC coding system (Anatomic Therapeutic Coding) will be used to identify exposure: all patients having been prescribed drugs for the treatment of diabetes (ATC code A10 and subcategories) will be retrieved and linked to the other databases: they will be followed via cancer and hospital discharge registries. The ICD10 codes will be used for outcome assessment: acute pancreatitis (K85), pancreatic cancer (C25) and thyroid cancer (C73), especially medullary thyroid cancer (Thyroid cancer is a distinct entity in the ICD10 and the tumour type can be determined by the ICD-0 code).

II.9.5 Study size (Sample size and study power)

A key consideration in designing studies is the requirement for a large enough number of events (pancreatitis, pancreatic cancer and thyroid cancer) to provide adequate statistical power to detect an effect. A conservative approach to estimating statistical power has been adopted, since the cumulative rate of events will be greatly increased as longer follow-up time is available.

Assuming an average prevalence of T2DM of 5% (Carstensen et al, 2008) for a total adult population (20+ years) in the 3 countries (Denmark, Norway and Sweden) of 15,000,000, our study population will reach approximately 750,000 subjects.

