In terms of exposure to GLP-1 RAs the literature search resulted into a very heterogeneous range of values. An estimation in the THIN database (based on records from a sample of UK GPs) up to the end of 2010 revealed that about 2% of type 2 diabetes patients were treated by GLP-1 agonists. This is likely to be underestimated, knowing that the UK system is usually slower in adopting new drugs. Several cohort studies in the US gave different estimations of exposure to GLP-1 RA: 17% (Garg et al, 2010) 11% (Doré et al, 2009), 2.6% (Romley et al, 2012), that may overestimate use in

Europe because adoption of new drugs is faster in the USA. Since liraglutide is manufactured and marketed by a Danish pharmaceutical company (Novo Nordisk), the proportion of type 2 diabetes patients treated with liraglutide in the Nordic countries is likely to be higher than that observed in the THIN database. We have therefore assumed that a proportion of 5 to 10% of the diabetic patients are exposed to GLP-1 RAs and the following sample size/power calculations are done for these 2 hypothetical values. Conservatively assuming an average follow up of one year for these patients and 5% of diabetics exposed to GLP-1, then 37,000 person-years (p-y) of total follow-up time will be eligible for this study by the end of 2011. Idem, if 10% of diabetics are exposed to GLP-1, then 74,000 person-years (p-y) of total follow-up time will be eligible for this study by the end of 2011.

The incidence rate of acute pancreatitis was estimated using age-specific data from Sandzen et al. (2009) for the period 1998-2003 among the Swedish population, weighted by the age distribution among the diabetic population (Diabetes in the UK April 2012 available at: http://www.diabetes.org.uk/Documents/Reports/Diabetes-in-the-UK-2012.pdf, Carstensen et al., 2008). Age specific incidence rate for pancreatic and thyroid cancer were derived from NORDCAN (www.dep.iarc.fr/nordcan.htm) and also weighted by the age distribution among the diabetic population. The estimated diabetes-age adjusted incidence rates are shown in Table **II.9.5.**1:

Table II.9.5.1: Projected age adjusted incidence rate

Outcome	Diabetes age adjusted incidence rate (per 100,000)
Pancreatitis	65.57
Pancreatic cancer	29.19
Thyroid cancer	6.13

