Under these assumptions, the minimal detectable risks (with 90% power and 95% confidence level, model: Poisson distribution) are shown in Table II.9.5.2 (sample size calculations using the methodology of Gu et al. 2008):

Table II.9.5. 2: Minimum detectable risk for one year of follow-up

Exposure to GLP-			
1 among	Acute	Pancreatic	
diabetics	Pancreatitis	cancer	Thyroid cancer
5%	1.80	2.40	5.63
10%	1.54	1.89	3.67

The database study will be completed in 2014. Figure II.9.5.2 shows the evolution of the minimum detectable risk with increasing years of follow-up, for 5% and 10% of exposure to GLP-1 among the diabetic population:

The estimation of sample size and study power for the primary and secondary objectives will be further defined after consultation with local Principal Investigators and external experts.

II.9.6 Data Management

In each centre data will be linked between the different data sources (population registry, prescription registry, hospital discharge registry, cancer registry) through an anonymized unique identification number. Linking the population registry, the prescription registry and the cancer registry has already been tested and proved to be effective through our previous database study (Boyle et al, 2012). However, linking with the hospital discharge registry requires a procedure preventing introduction of information bias in the study.

All patients identified to have had an anti-diabetic treatment in the prescription database (regardless of the type of medication taken) will be linked to the Hospital Discharge Registry. All discharge information will be retrieved for all the diabetic patients (with an

anti-diabetic prescription) and searched for codes or keywords that indicate a pancreatic related disease focussing on acute pancreatitis and pancreatic cancer.

Each national centre will be responsible for the data storage and data management of the individual-level data, following all national and European directives regarding the well being and rights of each study subject. Each centre has an excellent track record of successfully undertaking similar research respecting all moral and legal requirements.

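### Table II.9.5.2 overstates the detectable thyroid cancer risk by applying a large-sample formula to 2 to 5 expected cases, and its pancreatic cancer rate is not matched to the planned two-register outcome

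*Protocol*

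**What the plan says.** Protocol II.9.5 starts from the statement that "our study population will reach approximately 750,000 subjects". It takes 5% or 10% of them as exposed to a GLP-1 receptor agonist, with one year of follow-up each, giving 37,000 or 74,000 exposed person-years. Table II.9.5.1 gives planning rates per 100,000 of 65.57 for pancreatitis, 29.19 for pancreatic cancer and 6.13 for thyroid cancer. On the last two: "Age specific incidence rate for pancreatic and thyroid cancer were derived from NORDCAN".

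Table II.9.5.2 is computed "with 90% power and 95% confidence level, model: Poisson distribution", with "sample size calculations using the methodology of Gu et al. 2008". Whether the test is one- or two-sided is not said. The hypotheses in II.8 are directional, for example: "That adult patients prescribed GLP-1 RAs have an increased risk of pancreatic cancer when compared to patients prescribed other types of anti-diabetic drugs". II.9.7 plans hazard ratios with 95% confidence intervals.

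On ascertainment, II.9.3 first names the national cancer registers as the source for both cancers. It then treats under-registration of pancreatic cancer as a possible major problem and reports that, of 31,067 Swedish cases, "44% were registered in the Hospital Patient Discharge Register but not in the Cancer Registry". It concludes that "diagnoses of pancreatic cancer will be sought in both the Cancer Registry and the Hospital Patient Discharge Registry in each of the countries". II.9.4 describes cancer registration in Denmark and Norway as complete.

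The synopsis (Study Size) quotes the same rates, but at 80% power, with detectable risks of 1.53, 1.96 and 3.40.

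**The concern.** Two features of the cancer columns need checking. First, 37,000 person-years at 6.13 per 100,000 is about two expected cases, and a normal approximation to a count that small is unreliable. Second, the protocol widens the pancreatic cancer outcome because one register misses cases, yet the sizing section makes no matching adjustment to the rate and does not mention the issue.

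Pancreatic and thyroid cancer are both primary outcomes of the Database Study. The table is what a regulator would consult to judge which risks the study could have missed, so cells that are off affect how a null result is read. The missing sidedness adds to this: a reader who sees a 95% confidence level next to planned 95% intervals would probably assume a two-sided 5% test.

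**Working it through.** **Inputs.** Total 750,000 person-years (750,000 subjects, one year each; applying one year to the unexposed as well is my reading). Exposed t1 = 37,000 or 74,000, so unexposed t0 = 713,000 or 676,000. Rates, power and confidence level are as in II.9.5.

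**Step 1: reproduce the table.** Let d = t0/t1, m1 = R × rate × t1 (expected exposed cases at rate ratio R) and m0 = rate × t0. For an unpooled Wald test on the rate difference,

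power = Φ( (m1 − m0/d) / √(m1 + m0/d²) − z ).

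At one-sided 5% (z = 1.645) and 90% power (1.282), the first term must equal about 2.93.

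- Thyroid, 5% exposure, R = 5.63: null exposed cases 2.27, m1 = 12.77, m0 = 43.71, d = 19.27. The term is (12.77 − 2.27)/√(12.77 + 0.12) = 10.50/3.59 = 2.93.
- Thyroid, 10% exposure, R = 3.67: null exposed cases 4.54, m1 = 16.65, m0 = 41.44, d = 9.14. The term is (16.65 − 4.54)/√(16.65 + 0.50) = 12.11/4.14 = 2.93.

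Solved for R (5% / 10% exposure):

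| Outcome | Stated | Wald, one-sided 5% | Wald, two-sided 5% |
|---|---|---|---|
| Acute pancreatitis | 1.80 / 1.54 | 1.81 / 1.54 | 1.93 / 1.61 |
| Pancreatic cancer | 2.40 / 1.89 | 2.39 / 1.89 | 2.61 / 2.02 |
| Thyroid cancer | 5.63 / 3.67 | 5.63 / 3.67 | 6.52 / 4.14 |

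All six cells agree to about 0.01 one-sided. Of the standard large-sample variants tried (constrained variance, log-ratio, square-root, Schoenfeld; one- and two-sided; 80% and 90% power), this was the only match.

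**Step 2: exact check.** Given the total number of cases, the exposed count is binomial with null probability t1/750,000. Take the smallest critical value with tail probability at most 0.05 (one-sided) or 0.025 (two-sided), average the power over the Poisson total, and solve for R at 90%:

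| Outcome | Stated | Exact, one-sided | Exact, two-sided |
|---|---|---|---|
| Acute pancreatitis | 1.80 / 1.54 | 1.72 / 1.50 | 1.80 / 1.56 |
| Pancreatic cancer (29.19) | 2.40 / 1.89 | 2.17 / 1.80 | 2.30 / 1.89 |
| Thyroid cancer | 5.63 / 3.67 | 4.20 / 3.10 | 4.58 / 3.35 |

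Like for like (one-sided), the thyroid cells are too high by 5.63/4.20 − 1 = 34% and 3.67/3.10 − 1 = 18%. Full enumeration shows why: the nominal 5% Wald test has true size 0.011 and 0.020, and true power 0.969 and 0.956 at the stated ratios. Exact power at those ratios is 0.984 / 0.970 one-sided and 0.972 / 0.946 two-sided.

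**Step 3: pancreatic cancer rate.** Assume that 29.19 is cancer-registry incidence and that the Swedish shortfall applies to Sweden only. Weight by the diabetes counts in III.9.5: 493,210/1,049,810 = 0.4698. Then

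29.19 × (0.4698/0.56 + 0.5302) ≈ 40.0 per 100,000.

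The table's own formula (one-sided Wald) gives 2.12 / 1.73 against 2.40 / 1.89 stated. The exact test at that rate gives 1.96 / 1.66 one-sided or 2.08 / 1.74 two-sided.

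**The case against.** The best defence is that the table does what it says. It names a Poisson model, a cited two-rate method, 90% power and 95% confidence, and every cell follows from the stated rates and person-years. There is no slip of arithmetic, and whether the cited method prescribes this formula cannot be checked here. That stands: a reader might infer that both cancer columns are wrong on the protocol's own terms, and the documents do not support it. What is in question is the choice of approximation for thyroid cancer and the choice of input for pancreatic cancer.

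It can also be said that both effects err on the cautious side, in a section that calls its approach conservative, covers a single year of follow-up and promises further refinement. The direction is as described. But the ground II.9.5 gives for caution is that events will accumulate with longer follow-up. It does not mention an approximation that fails at these counts, and a reader cannot see the extra margin.

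On pancreatic cancer, no section says what NORDCAN contains, so a shortfall in 29.19 is an inference. A reader might also apply the 44% to all three countries, giving 29.19/0.56 = 52.1 per 100,000 and detectable risks of 1.94 / 1.62. The figure is reported for Sweden alone, and II.9.4 describes Danish and Norwegian registration as complete, so that scenario has no documentary support.

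Finally, the pancreatitis column may look confirmed because the exact two-sided values (1.80 / 1.56) nearly equal the stated ones. That compares a one-sided Wald figure with a two-sided exact one; the two differences happen to cancel.

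**Conclusion.** The point holds in two limited parts.

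**Thyroid cancer.** The stated 5.63 / 3.67 are not 90%-power values. They should be about 4.20 / 3.10 at one-sided 5%, or 4.58 / 3.35 at two-sided 5%. The cells are too high whichever sidedness was meant, so the study is better able to detect a thyroid cancer risk than the table says. This rests only on the protocol's own rates and person-years and the one-year reading for the unexposed.

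**Pancreatic cancer.** The planning rate and the two-register outcome are not aligned. The size is conditional: with a Sweden-only shortfall and a NORDCAN rate limited to cancer registration, the table's formula gives 2.12 / 1.73. With no shortfall, 2.40 / 1.89 stand under that formula. No single corrected figure can be given.

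The unstated sidedness affects the whole table. These faults misstate a planning quantity; they do not undermine the data, the conduct or the planned hazard-ratio analysis.

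**What to change.** 1. State in II.9.5 whether the test is one- or two-sided, and at what alpha.
2. Recompute all six cells of Table II.9.5.2 with one exact Poisson test at that alpha, rather than mixing methods or sidedness between columns.
3. Show pancreatic cancer over rates from 29.19 (no shortfall) to about 40.0 per 100,000 (Swedish shortfall only), and say whether the NORDCAN rate includes discharge-only cases. Label any higher rate as an assumption.
4. In II.9.3, reconcile the sentence naming only the cancer registers with the two-register search for pancreatic cancer.
5. Recompute the synopsis figures on the same basis, at a power level reconciled with the table. The 90% values cannot simply be copied into a synopsis that states 80%. The table's formula at one-sided 5%, 80% power and 37,000 person-years gives 1.66, 2.11 and 4.54, not the synopsis's 1.53, 1.96 and 3.40.

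The cost is a recalculation, some text edits and a redrawn Figure II.9.5.2. Any change to the pancreatic cancer rate should also be carried to Table III.9.5.2, which uses 29.19. No data collection or study conduct changes.

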
III Patient Registry of Lixisenatide Use in Adult Type 2 Diabetes

Format and Content of Study Protocol

III.1 Title

Patient Registry of Lixisenatide Use in Adult Type 2 Diabetes

III.2 Marketing Authorization Holder

The marketing authorization holder (MAH) is Sanofi.

III.3 Responsible Parties

Principal Investigator	*[name] PhD DSc FRSE FFPH FRCPSG FRCP FMedSci
Senior Investigator	*[name] MD PhD
Study Coordinator	*[name] MSc/MEng
Study Statisticians	*[name] PhD
-	*[name] PhD

Local Investigator, Denmark	[name] MD
Local Investigator, Denmark	[name] PhD
Local Investigator, Norway	[name] MD PhD
Local Investigator, Sweden	[name] MD PhD

*A brief *Curriculum Vitae* is attached as Appendix IV.

Title Patient Registry of Lixisenatide Use in Adult Type 2 Diabetes

Rationale and Background. GLP-1 RAs have been a focus of attention since the signalling of certain (rare but serious) adverse effects reported with their use: pancreatitis, pancreatic cancer and thyroid cancer (especially medullary carcinoma). A new GLP-1 RA (i.e. lixisenatide) treatment for type 2 diabetes will soon be available on the market. An active surveillance approach is more useful for monitoring products after launch by providing a system for reporting these adverse effects and by collecting information on the exposed population.

Research Question and Objectives. In the context of pharmacovigilance activity of the EU RMP (European Union Risk Management Plan), it has been agreed with the European Medicines Agency (EMA) to develop a registry to monitor the occurrences of events of interest including acute pancreatitis, pancreatic cancer and thyroid cancer, especially medullary carcinoma of the thyroid, among adult type 2 diabetes patients treated with lixisenatide.

Study Design This will take the form of a Patient Registry involving patients with lixisenatide in Denmark, Norway and Sweden.

Population Diabetic patients prescribed with lixisenatide in Denmark, Norway and Sweden since the day on which lixisenatide was approved for use.

Variables For each patient, information regarding all anti-diabetic medications prescribed in the study period will be recorded together with basic information such as age and gender. Patients who develop cancer will be identified as will anyone who is diagnosed with pancreatitis, and their complete clinical information will be retrieved and collected from existing national registers and databases annually: smoking history, a previous diagnosis of Multiple Endocrine Neoplasia (especially MEN1), chronic pancreatitis, duration of diabetes, gallstones, prior use of other anti-diabetics, alcohol intake, obstruction of the pancreatic duct, radiation treatment to the head and neck, iodine intake, hormonal and reproductive treatment, diagnosis of Multiple Endocrine Neoplasia type 2 (MEN2), history of goitre or benign thyroid nodules, history of cancer, and family history of medullary thyroid cancer.

Data Sources Patients will be identified in the National Prescription Database. They will be linked to the National Death Indices, National Cancer Registries and National Hospital Discharge schemes to identify cases of cancer, pancreatitis and anyone who has died. Clinical data for all patients with the outcome of interest will also be retrieved from National Hospital Discharge schemes. Additional data will be collected from other (country specific) available data sources.

Study Size For a 1% exposure to lixisenatide among diabetic patients, thus 38 expected cases of pancreatitis, the power of the study in order to detect an observed vs

expected ratio of pancreatitis of 1.5 will be of 83% (significance level=0.05). Futhermore, the study will be able to detect an observed vs expected ratio of pancreatic cancer of 1.5 with 59% power (significance level=0.05), and an observed vs expected ratio of 2 with 92% power (significance level=0.05). However, for 1% exposure to lixisenatide, the study is underpowered to detect these same ratios of thyroid cancer, it will be able to detect with power of 92% an observed vs expected ratio of 2 (significance level=0.05) for 5% exposure to lixisenatide among the diabetic population.

Data analysis Descriptive analysis will be performed and total follow-up time for lixisenatide users will be calculated. For pancreatitis, pancreatic cancer and thyroid cancer, the expected number of cases will be estimated annually after launch using the background rates obtained from the retrospective databases study. If the observed number of cases for the events of interest, respectively, is significantly higher than the expected number of cases, further investigation may be warranted following discussion with the regulatory authorities.

Milestones The registry will be initiated after the launch of lixisenatide and preparations will begin with immediate effect to ensure that the systems are in place prior to launch. Status reports will be submitted to the Agency annually, together with the RMP update as planned. Final report will be submitted to the Agency at the end of the registry.

III.5 Amendments and Updates

This is the initial protocol and any amendments will be placed here in a timely manner.

III.6 Milestones (events in months)

The registry will be initiated after the launch of lixisenatide and preparations will begin with immediate effect to ensure that the systems are in place prior to launch. Status reports will be submitted to the Agency annually, together with the RMP update as planned. Final report will be submitted to the Agency at the end of the registry.

However, if a sufficient number of participants are captured for any outcome(s) of interest earlier before the end of registry, the final data analysis for the particular outcome(s) will be started immediately and the study report will be made available within 12 months.

Start of preparatory	Т0	Development of draft Protocol	
phase	T0+1	Meeting with Sanofi Global Pharmacovigilan	
		and Epidemiology, Regulatory, and Medical	
		Affairs	
	T0+1	Establishment of Scientific and Steering	
		Committee	
	T0+2	Meeting of local Principal Investigators to refine protocol	
	T0+3	Protocol agreed and submitted to CHMP EMA	
	T0+6	Development of data collection module	
	T0+7	Synthesis of background information on	
		disease rates in populations	
	T0+8	Preliminary Pilot Testing of data collection and	
		data transfer	
	T0+9	Final agreement on Protocol from CHMP	
	T0+9	IRB/Ethics Approval	
	T0+10	Registry ready to launch	
Start of data collection	Date of mark	ket authorization for Lixisenatide – T	
End of data collection	2018		
Study progress reports	Yearly		
Interim reports	Yearly		
Final study report	2017 for Acute pancreatitis		
	2019 for pancreatic and thyroid cancer		

III.7 Rationale and Background

GLP-1 RAs have been a focus of attention since the signalling of certain (rare but serious) adverse effects reported with their use: pancreatitis, pancreatic cancer and thyroid cancer (especially medullary carcinoma, a rare tumour of the thyroid gland).

Glucagon-like peptide 1 receptor agonist (GLP-1 RA) is a new class of blood glucose lowering drugs indicated in the treatment of type 2 diabetes mellitus (T2DM). It is an agonist molecule to the incretin (gastrointestinal hormone) GLP-1 which stimulates glucose-dependant secretion of insulin. GLP-1 is rapidly inactivated by the dipeptdyl peptidase-1 (DPP-4) (half life of about 2 minutes), hence the need for a GLP analogue or agonist with greater resistance to DDP-4 degradation. GLP-1 regulates glucose levels by stimulating glucose-dependent insulin secretion and biosynthesis, and by suppressing glucagon secretion, delayed gastric emptying and promoting satiety.

There are currently 2 GLP-1 RA products on the market, one of which (exenatide) is available in two formulations (Byetta and Bydureon):

- Exenatide (also Exendin-4) marketed as Byetta by Amylin Pharmaceuticals, Inc., (San Diego, California, United States of America was launched in 2005 in the USA and approved in 2006 in the European Union and is administered subcutaneously twice daily; Exenatide marketed as Bydureon by Amylin Pharmaceuticals, Inc., (San Diego, California, United States of America) was approved on the market in 2012 and is administered subcutaneously once weekly.
- Liraglutide, marketed as Victoza by Novo Nordisk, Inc. (Copenhagen, Denmark). • Liraglutide was approved by the European Medicines Agency (EMA) in July 2009 and by the United States Food and Drug Administration (FDA) in January 2010. Liraglutide, a once-daily glucagon-like peptide-1 receptor agonist, is approved for use as monotherapy in the USA and Japan (but not in Europe or Canada) and in combination with selected oral agents (all regions) for the treatment of patients with type 2 diabetes. Guidance from local advisory bodies is emerging on the most appropriate place for liraglutide in the treatment pathway. It is apparent from its phase 3 clinical trial programme that liraglutide provides superior glycaemic control compared with that achieved with other antidiabetic agents used early in the treatment pathway (e.g. glimepiride and sitagliptin). Key additional benefits include a low incidence of hypoglycaemia and clinically relevant weight loss, although these benefits may be ameliorated by concomitant sulphonylurea treatment and, in the case of hypoglycaemia, reduction of the sulphonylurea dose may be necessary.

Safety concerns

GLP-1 receptor agonists have been demonstrated to have impact on glycaemic control, to be associated with weight loss and to carry a low risk of hypoglycaemia (Bergenstal

et al, 2012; Scott et al, 2012; Nauck et al, 2012; Alves et al, 2012; Gough, 2012; Scott et al, 2012; Shyangdan et al, 2011). However, these drugs have been a focus of attention since they may be associated with the occurrence of certain (rare but serious) adverse: acute pancreatitis, pancreatic cancer and thyroid cancer (especially medullary carcinoma of the thyroid).

Acute Pancreatitis

Spontaneous (post-marketing) reports of acute pancreatitis among type 2 diabetes patients on GLP-1 agonists were submitted to the FDA Adverse Event Reporting System [FDA alert: information for healthcare professionals: exenatide (marketed as Byetta). FDA: Postmarket Drug Safety Information for Patients and Providers, available at: http://www.fda.gov/Drugs/DrugSafety/PostmarketDrugSafetyInformationforPatientsand Providers/ucm124713.htm]. Since the introduction on the market in 2005 until 8/18/2008, 36 cases of acute pancreatitis were reported in patients taking Byetta. As a result of these spontaneous results the FDA required the manufacturer to include a warning for the risk of pancreatitis on the prescribing information of exenatide.

Also, at the introduction on the market of the new molecule liraglutide (marketed as Victoza), patients were warned about the potential risks of pancreatitis, as there was a 4:1 imbalance of the pancreatitis cases in patients using Victoza compared to patients using another diabetes medicine in 5 clinical trials [source: http://www.fda.gov/Drugs/DrugSafety/PostmarketDrugSafetyInformationforPatientsand Providers/ucm198543.htm]

However the preclinical and clinical evidence over the mechanism linking GLP-1 RA and acute pancreatitis is conflicting (Anderson et al, 2010; Elashoff et al, 2011; Drucker et al 2011). Preclinical studies showed equally a negative effect of incretin based drugs on the risk of developing pancreatitis (Matveyenko et al, 2009; Nachani et al, 2010) as well as a null effect or a positive effect (Engel et al, 2010; Tatarliewicz et al, 2010).

The clinical data are equally contradictory. A recent meta-analysis was carried out in order to assess the risk of acute pancreatitis and overall cancer with use of exenatide and liraglutide separately (Alves et al, 2012). The Summary Odds Ratio (SOR) based on 13 studies of exenatide that reported acute pancreatitis outcome was found to be 0.84 [95% CI, 0.58; 1.22]. The 13 studies included 3 cohort studies [Doré et al.2009; Doré et al.2011; Garg et al, 2010; Wenten et al, 2012) and 10 randomized controlled trials out of which 6 reported zero cases of pancreatitis, hence the odds ratio was zero. The overall Summary Odds Ratio based on 12 RCT of liraglutide that report acute pancreatitis outcome was found to be 0.97 [95% CI, 0.21; 4.39], out of which 8 studies reported zero cases of acute pancreatitis. There have been no post-market observational studies for liraglutide and acute pancreatitis so far. These results are weakened by limitations such as the fact that they are based on small studies, underpowered to detect rare adverse effects and of short duration.

A number of other studies have been reported:

- Romley et al (2012) conducted a study of exenatide therapy and the risk of pancreatitis and pancreatic cancer in a privately insured population. This is a retrospective cohort study on type 2 DM patients with employer provided health insurance from 2007 to 2009. Among the 268,561 patients included in the study, only 2.6% used exenatide. The hospitalization rate for acute pancreatitis among patients who used at least one exenatide prescription was 1.96 per 1000 patients compared to 2.49 per 1000 patients who never used exenatide (p-value = 0.167).
- MacConell et al (2012) examined the safety and tolerability of exenatide twice daily in patients with type 2 diabetes with an integrated analysis of 5594 patients from 19 placebo-controlled and comparator-controlled clinical trials This is an integrated analysis of 19 RCT carried out by the manufacturer. The incidence rates for pancreatitis were not statistically different between groups.
- Elashoff et al (2011) reported on the disproportion of the FDA-AERS database of reported adverse events showed an increased risk of acute pancreatitis with exenatide: OR = 10.68 (p-value vs control drugs=2 x 10e-16). However, this must be interpreted bearing in mind the known limitations of this database (e.g. http://www.ncbi.nlm.nih.gov/pubmed/15317031).

The literature can be summarised by observing that the small number of reported events and other design limitations of the studies currently available does not allow for clear conclusions to be drawn, one way or another, at the present time.

Pancreatic Cancer

Besides observing a high number of pancreatitis cases, Elashoff et al (2011) also reported on pancreatic cancer in patients treated with exenatide $[OR=2.95 (p \text{ value vs control drugs}=9 \times 10e-5)]$). There are no further clinical studies that address this issue. Experimental data show that GLP-1 agonists increase beta-cell mass in rodents, But human trials do not support the rodent data (Brubaker et al, 2009)..

Thyroid Cancer

The rodent calcitonin producing C-cell expresses GLP-1Rs, and sustained GLP-1R activation results in increased calcitonin secretion, C-cell hyperplasia and medullary thyroid cancer, predominantly in rats. In contrast, C cells within the monkey and human thyroid gland exhibit lower levels of GLP-1R expression, and prolonged administration of liraglutide at very high doses does not produce C-cell proliferation in monkeys (Drucker et al, 2011; Bjerre Knudsen et al, 2010).

A review on the association between glucagon-like peptide-1 receptor agonists and thyroid cancer (Chiu et al., 2012) concludes that GLP-1 agonists might increase the risk of thyroid C-cell pathology in rodents, but its risk in humans awaits confirmation.

Therefore, the effects of GLP-1 on human cancer development are overall unknown and difficult to be extrapolated from pre-clinical studies. In addition, the small number of cases and the lack of biological plausibility raise doubts between the use of GLP-1 agonists and the occurrence of cancer (pancreatic, thyroid or overall). Therefore longer-term, better designed epidemiological studies are required, in order to assess any risks associated with GLP-1 RA use.

Design of Investigative Study

Two studies have been prepared and the patient registry is presented below. The rationale behind both studies revolves chiefly around the concept of performing the Registry study in the same populations where the incidence rates of acute pancreatitis, pancreatic cancer and thyroid cancer, in particular medullary thyroid cancer in adult patients with type 2 diabetes treated with GLP-1 agonists (i.e., exenatide and liraglutide) and other anti-diabetics are established.

Very limited background information is available in the literature for the incidence rates of acute pancreatitis, pancreatic cancer and (medullary) thyroid cancer in adult type 2 diabetes patients treated with GLP-1 agonists (i.e., exenatide and liraglutide) and other anti-diabetics. Therefore, the data from such a study will help contextualize these events expected to be observed in the patient registry of lixisenatide.

"On 15 November 2012, the Committee for Medicinal Products for Human Use (CHMP) adopted a positive opinion, recommending the granting of a marketing authorisation for the medicinal product Lyxumia. The active substance of Lyxumia is lixisenatide, a glucagon-like-peptide-1 (GLP-1) analogue medicinal product. Like native GLP-1, lixisenatide stimulates insulin release from the pancreatic islets, suppresses glucagon secretion, delays gastric emptying and reduces body weight. A pharmacovigilance plan for Lyxumia will be implemented as part of the marketing authorisation." (from EMA - Lyxumia).

